12. STATISTICS

12.1 Sample Size and Power Calculations

Primary Analysis:

The primary endpoint is a composite endpoint comprising investigator and subject assessments of treatment effectiveness using the FWS. Composite endpoint treatment success (CETS) is defined as ≥ 2 point reduction in FWS score at maximum from achieving a score of 0 or 1 at the visit week 4 relative to baseline based on investigator assessment and subject assessment. Thus, a subject is a CETS “Responder” only if both investigator- and subject-rated success criteria are satisfied at the visit 4 weeks after baseline.

The primary analysis of efficacy is the proportion of responders in the BoNT/A-DP treatment group compared with the placebo treatment group. For superiority testing of BoNT/A-DP compared with placebo, the following assumptions for the sample size calculation will be used:

Item	Assumption	Comments
Underlying test	Fisher’s Exact Test	Standard test for a response parameter for small numbers
Randomization scheme	3:1	More active treatment subjects to enlarge safety data base
Power $1-\beta$	90%	
Significance level (α)	0.025 one-sided	
Response Arm BoNT/A-DP	60%	From the range of observed response rates, a more conservative value of 60% has been chosen
Response Arm Placebo	10%	Conservative value
Software		The sample size calculation was performed using the software nQuery Advisor® 7.0.

Based on these assumptions, 42 subjects in the BoNT/A-DP arm and 14 subjects in the placebo arm are required, i.e. 56 subjects in total. This is a very small sample size and not sufficient for a detailed evaluation of the data, including subgroup analyses. Furthermore, the response rate could not be estimated with sufficient precision. A

two-sided CI of 95%, and a distance from the CI limit of about 4.5% could be achieved with a sample size of 450 subjects in the BoNT/A-DP group. We propose a 3:1 randomization of BoNT/A-DP (525 subjects) to placebo (175 subjects), which we believe is adequate for a precise estimate of response rate and for post-hoc sensitivity analyses (i.e. treatment-by-center and other subgroup analyses), also taking into account a drop-out rate.

In total, 700 evaluable subjects will be enrolled. Applying a 10% drop out rate would result in a total number of about 630 subjects.

12.2 Data Sets and Analysis Cohorts

Safety Analysis Set (SAF):

All randomized subjects who received at least one injection with study medication (independent of whether it is BoNT/A-DP or placebo) will be valid for the SAF. Within the SAF, a subject will be considered for the treatment actually received and not for the treatment assigned by randomization, if different. The SAF will be used for the evaluation of the safety assessments.

Full Analysis Set (FAS):

The FAS includes all subjects included in the SAF. Within the FAS, a subject will be considered for the treatment assigned by randomization and not for the treatment actually received, if different, i.e. following the intent-to-treat (ITT) principle. The FAS will be used for the evaluation of the efficacy assessments. The FAS serves as the primary efficacy analysis set.

Modified Full Analysis Set (MFAS):

The FAS includes all subjects included in the SAF who had a baseline (visit 1 at day 0) and at least one post-dose in-clinic assessment with the FWS by either the investigator or the subject on visits at weeks 1, 2 or 4. Within the MFAS, a subject will be considered for the treatment assigned by randomization and not for the treatment actually received, if different, i.e. following the intent-to-treat (ITT) principle. The MFAS will be used for the evaluation of the efficacy assessments.

Per-protocol Analysis Set (PP):

The PP includes all subjects who had no significant protocol deviations and an in-clinic assessment with the FWS by the investigator and the subject at baseline (day 0) and at the week 4 visit. For the PP, all subjects will be assigned to the treatment actually received. The PP will only be analyzed for main efficacy outcome measures.

Data Review Meeting:

Subjects will be assigned to the SAF, FAS, MFAS, and PP during a data review meeting (DRM). Further details on the analysis sets, criteria for the PP, and the DRM will be specified within the statistical analysis plan (SAP). Details for and decisions on protocol deviations will be specified in a classification meeting taking place between database lock and unblinding. Corresponding documentation should be held outside of the SAP.

12.3 Procedure for Accounting for Missing, Unused, and Spurious Data

Analyses will be performed by visit. For responder analyses on visits at week 4 and week 12, missing in-clinic assessments (investigator or the subject) with the FWS at baseline or week 4 and week 12 visits will be assigned as being non-responders.

As sensitivity analyses, the following additional approaches for handling of missing values will be applied:

- Analysis on observed values only, i.e. missing values will be excluded from analysis.
- Last observation carried forward (LOCF)
- Tipping point analysis: each missing value will be assigned to either a response or non-response, so that all possible combinations of replacing 1 or more missing values within each treatment group will be analyzed. p-values will be calculated for each combination and graphically displayed using a scatter plot.

12.4 Methods of Analysis

12.4.1 Primary Outcome Measure

Primary Analysis:

The proportion of subjects (responders) meeting the primary endpoint with a FWS score of 0 or 1 and an improvement ≥ 2 points in FWS score (at maximum frown) at week 4 visit relative to baseline, based on both the investigator and the subject

in-clinic assessments will be analyzed using the Cochran-Mantel-Haenszel test (with stratification variable site; small sites with less than 3 placebo subjects will be combined) using a significance level (α) of 0.025. The hypothesis to be tested is:

$$H_0: p_{BoNT/A-DP} \leq p_{Placebo}$$

$$H_1: p_{BoNT/A-DP} > p_{Placebo}$$

The Cochran-Mantel-Haenszel test will be applied using SAS procedure Proc Freq (using the General Association Statistic). The one-sided p-value will be derived by halving the two-sided p-value delivered by the SAS procedure. Superiority of BoNT/A-DP over placebo will only be concluded if, besides statistical significance (one-sided p-value ≤ 0.025), the proportion of responders in the BoNT/A-DP treatment group is higher than for the placebo treatment group.

The FAS will serve as the primary analysis set.

Subjects with missing investigator or subject in-clinic assessments with the FWS at baseline or visit week 4 will be assigned as being non-responders.

Additional Analyses on the Primary Endpoint Variable:

Further analyses on the primary endpoint variable are exploratory. A one-sided Pearson χ^2 -test will be applied. Two-sided CI of 95% for the responder rates in the BoNT/A-DP and the placebo treatment groups will be calculated using Wilson scores. Treatment-by-center interaction will be tested using the Breslow-Day test for homogeneity of the odds ratios. The CIs will also be calculated for the additional analyses as listed in the following:

- The primary endpoint measure using the observed values only, i.e. missing investigator or the subject in-clinic assessments with the FWS at baseline or week 4 visit will be excluded from analysis but not assigned as being non-responders.
- The primary endpoint measure using the MFAS and the PP.
- The primary endpoint measure applying the LOCF for week 4 visit.
- Subgroup analysis by geographic region, country, and site.
 - Subgroup analyses will be conducted for geographic region (US/EU), country, and site. Sites with less than 3 placebo subjects will be combined. The χ^2 -test will be applied for each subgroup. In case of a total number of observations below 30, or in case of at least one cell frequency below 5, Fisher's exact test will be used instead of the χ^2 -

test. Stratified analyses applying the Cochran-Mantel-Haenszel test will also be conducted using factor geographic region and country.

- Subgroup analysis by subjects with previous use of botulinum toxin versus naïve subjects.
 - Subgroup analyses will be conducted for subjects with treatment with any serotype of botulinum toxin for any indication versus naïve subjects. The χ^2 -test or Fisher's exact test (see above corresponding criteria to use Fisher) will be applied for each subgroup. No stratified analysis using factor pre-treated/naïve subjects is currently planned.

12.4.2 Secondary Outcome Measures

Key Secondary Analyses:

The testing of the 5 key secondary endpoints will be performed with appropriate multiplicity control based on the FAS population. The results of each test result will only be considered confirmatory if the previous test in the order showed a confirmatory result at a one-sided significance level of 0.025. If the one-sided p-value is larger than 0.025 for any of the tests, the results of the subsequent tests will only be considered exploratory, and not confirmatory. The application of this hierarchical approach keeps the global significance level to 0.025 one-sided and requires no further adjustment of the significance level.

The following order of tests will be defined:

- Primary endpoint (composite endpoint)
- Key secondary endpoint 1
- Key secondary endpoint 2
- Key secondary endpoint 3
 - 3.1: The investigator's in-clinic assessments
 - 3.2: The subject's in-clinic assessments
- Key secondary endpoint 4
- Key secondary endpoint 5
 - 5.1: The modified Skindex-16 (GL-QoL) Emotional domain
 - 5.2: The modified Skindex-16 (GL-QoL) Functioning domain

Analysis of key secondary endpoint 1: The percentage of responders at maximum frown (as defined above) at week 12 (after the first treatment with BoNT/A-DP or placebo).

The same analyses, inclusive of the additional exploratory analyses, as described for the primary endpoint will be conducted.

Analysis of key secondary endpoint 2: The percentage of responders at week 16 (after the first treatment).

The analysis of the week 16 visit will be conducted on observed values only, i.e. missing investigator or the subject in-clinic assessments with the FWS at baseline or week 16 visit will be excluded from analysis but not assigned as being non-responders. Subjects who were re-treated before visit week 16 are considered to be non-responders.

In addition, the same analyses, inclusive of the additional exploratory analyses, as described for the primary endpoint will be conducted.

Analysis of key secondary endpoint 3: The proportion of subjects with a > 1 point reduction in FWS score at rest at week 4 in the first treatment cycle, based separately on the investigator and the subject in-clinic assessments

In general, the same statistical analyses, inclusive of the additional exploratory analyses as described for the primary endpoint, will be conducted.

The analysis using the investigator's in-clinic assessment will be conducted first with respect to the hierarchical order of key secondary endpoints, with the analysis using the subjects's in-clinic assessment second.

The analysis on the investigator's in-clinic assessment will be conducted only for subjects who have an investigator's in-clinic assessment of a FWS score at rest > 1 at baseline. This will similarly be applied for the analysis of the subject's in-clinic assessment.

Subjects with missing investigator in-clinic assessments at baseline or week 4 visit will be assigned as being non-responders for this endpoint. This will similarly be applied for the subject's in-clinic assessment.

Analysis of key secondary endpoint 4: The percentage of responders at week 20 or later (after the first treatment).

The analysis of visit week 20 will be conducted on observed values only, i.e. missing investigator or the subject in-clinic assessments on FWS at baseline or visit week 20 will be excluded from the analysis but not assigned as being non-responders. Subjects who were re-treated before visit week 20 are considered to be non-responders.

In addition, the same analyses, inclusive the additional exploratory analyses as described for the primary endpoint, will be conducted (for subgroups also).

Analyses of other visits after first treatment but before re-treatment are exploratory only. Additional exploratory analyses, as described for the primary endpoint, will not be conducted, with the exception of the calculation of 95% CIs.

Analysis of key secondary endpoint 5: The extent of change in psychological impact (emotional and social functioning, and concerns relating to glabellar lines) at week 4 after the first treatment, in the BoNT/A-DP group in comparison with placebo, relative to baseline, as assessed by the modified Skindex-16 (GL-QoL) and the FACE-Q Appraisal of Lines Between Eyebrows and FACE-Q Age Appraisal VAS.

The modified Skindex-16 (GL-QoL) and FACE-Q Appraisal of Lines Between Eyebrows scale and FACE-Q Age Appraisal VAS scales will be analyzed according to the foreseen analysis approach of these tools, as described below.

Emotional and Social Functioning

The modified Skindex-16 (GL-QoL) Emotional and Functioning domain and overall scores will be derived in accordance with the Skindex-16 manual, adapted for the GL-QoL. The scores will be standardized on a scale from 0 (no impact) to 100 (maximal impact); a scale score is the average of responses to items addressing a construct. Domain and overall scores will be calculated if at least two of each of three domain items are present. The absolute change from baseline (measured on the screening visit) will be calculated for the domain and overall scores and statistically compared between the treatment groups using the Wilcoxon Rank Sum test (or t-test). Estimates of ‘mild’, ‘moderate’, and ‘severe’ psychological impact, and of the minimal clinical important difference, will be used to aid interpretation of scores.

The analysis will be conducted with respect to the hierarchical order of key secondary endpoints; the analysis using the Emotional domain first, the Functioning domain second, and the overall score third. All analyses will be conducted on observed values only, i.e. missing domain and overall scores will be excluded from analysis; no imputation of missing domain and overall scores will be performed.

Concerns Relating to Glabellar Lines

The FACE-Q Appraisal of Lines Between Eyebrows scale and FACE-Q Age Appraisal VAS scores will be derived in accordance with the developers’ instructions and missing data treated accordingly. The absolute change from baseline (measured

on the screening visit) will be calculated for each scale and statistically compared between the treatment groups using the Wilcoxon Rank Sum test. All analyses will be conducted on observed values only, i.e. missing scale scores will be excluded from analysis; no imputation of missing scores will be performed. This analysis will be conducted with respect to the hierarchical order of key secondary endpoints as well; the analysis of FACE-Q Appraisal of Lines Between Eyebrows scale first, followed by the analysis of FACE-Q Age Appraisal VAS scores.

Exploratory Analyses

Exploratory analyses of modified Skindex-16 (GL-QoL) domain and overall score and FACE-Q Appraisal of Lines Between Eyebrows scale and FACE-Q Age Appraisal VAS will also be conducted using the MFAS and the PP population. Subgroup analysis by geographic region, country, and site, or by subjects with previous use of botulinum toxin versus naïve subjects will not be conducted.

Additional Secondary Analyses:

The additional secondary efficacy endpoints will be analyzed applying the appropriate statistical method for the comparison of both treatment arms. For proportions, the Cochran-Mantel-Haenszel test (with stratification variable site) and the Pearson χ^2 -test will be applied. In case of a total number of observations below 30, or in case of at least one cell frequency below 5, Fisher's exact test will be used instead of the χ^2 -test. Two-sided 95% CIs for response rates will be calculated, where appropriate. Additionally the cumulative proportions of effects at weeks 1, 2, and 4 will be calculated.

All endpoints, with exception of “responder” 4 weeks after re-treatment, will be analyzed for the first treatment cycle only. The analysis of “responder” 4 weeks after re-treatment will be conducted on observed values only, i.e. subjects with missing investigator or the subject in-clinic assessments on FWS week 4 or at the preceding end of the cycle visit will be excluded from analysis. Subjects who were treated with placebo during the first treatment cycle are excluded from the analysis of this endpoint, but not assigned as being non-responders. A two-sided McNemar test (using a significance level of 0.05) will be used to compare the response proportions between week 4 re-treatment visit and at the preceding end of the cycle visit. This endpoint will be separately analyzed for each open label extension cycle.

Besides the FAS population for the analysis with multiplicity control, the analyses of these endpoints will also be based on the MFAS and the PP population. For all analyses, a one-sided significance level of 0.025 will be used, if not stated otherwise.

Additional exploratory subgroup analyses by geographic region, country, and site, or by subjects with previous use of botulinum toxin versus naïve subjects, will not be conducted for additional secondary analyses.

Secondary Safety Endpoints:

No statistical testing methods will be applied to statistically evaluate the differences on safety variables between treatment groups. Safety endpoint variables will be analyzed descriptively only.

Analysis of secondary safety endpoint 1 (adverse events):

Adverse events will be separated to pre-treatment AEs and TEAEs. TEAEs are defined as all AEs with onset or worsening (increase in severity) after receiving first dose of study medication (independent of whether it is BoNT/A-DP or placebo). If it cannot be determined whether an AE is treatment-emergent due to a partial onset date, then it will be counted as such.

TEAEs will be analyzed overall (for BoNT/A-DP or placebo), and for BoNT/A-DP treatment group additionally separately per first treatment cycle or open label extension phase: events starting on or after first treatment up to before open label extension (first cycle), and events starting on or after re-treatment until end of study (open label phase). If it cannot be determined whether an AE started during the first treatment cycle or the open label extension phase due to a partial onset date, then it will be counted as having started during first treatment cycle.

Events of subjects who started the first treatment with placebo but then entered the open label extension for re-treatment with BoNT/A-DP will be considered to placebo for the first cycle and to BoNT/A-DP for the open label phase.

Treatment-emergent adverse events will be summarized by system organ class (SOC) and preferred term (PT) (MedDRA). The number of events, as well as the number and rate of affected subjects will be reported. TEAEs (SOC and PT) will also be summarized by seriousness, severity, relationship to study medication, and relationship to procedure. Treatment-emergent AESIs will be tabulated separately.

Analysis of secondary safety endpoint 2 (antibody formation):

The presence of antibodies will be summarized by counts and percentages of subjects by treatment group and time point. For the subgroup of subjects with a sample test positive for anti-drug antibodies, all analyzed samples will be analyzed descriptively by counts over time as well.

Analysis of secondary safety endpoint 3 (laboratory data, vital signs, ECG):

All laboratory values will be classified as normal or abnormal according to the central laboratory normal ranges and indicated as clinically significant (CS) or not clinically significant (NCS) by the investigator. Quantitative laboratory values will be summarized with means, standard deviations, medians, minima and maxima at baseline and over time and of absolute changes from baseline. Categorical variables will be summarized by counts and percentages of subjects in corresponding categories. Shift tables illustrating changes with respect to the central laboratory normal ranges and the investigator assessment between baseline and post-baseline visits will be created: Number and percentage of subjects with normal, CS and NCS laboratory values.

The analyses of variables for vital signs will focus on the evaluation of the change from baseline to the scheduled time points after baseline. Descriptive analysis with means, standard deviations, medians, minima and maxima of the time course and of changes from baseline to each post-baseline visit will be presented.

Normal/abnormal shift tables will be created for categorical variables of the overall ECG interpretation.

An additional safety evaluation will be performed by defining cycle 2 day 0 as baseline for subjects who switched from placebo to BoNT/A-DP.

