TC = telephone contact: including assessment of concomitant medication, AEs and AESIs¹⁵ (as per AESI manual) on weeks 2 and 8 of each open-label cycle (visits 9, 11, 14, 16, 19 and 21). If an AESI is reported during a telephone contact, subjects will be asked to come to the site for further assessment including a targeted physical examination as soon as possible) * Visit numbers correspond with specific treatment and assessments. If subjects are not eligible for re-treatment at the "Evaluation for Re-treatment" visit, they will return at 4 weekly intervals thereafter, until they are eligible for treatment. The subsequent visit number for the cycle will remain the same, but will be amended with "a, b, c" etc., corresponding to the time extended (at 4 weekly intervals) in that treatment cycle. For example, the first evaluation for re-treatment is at visit 7, week 12, however for subjects who are not eligible at week 12, but at week 16, this visit will be denoted "visit 7a", while "visit 7b" will denote week 20 in the first cycle and "visit 7c" will denote week 24 etc., with each additional letter corresponding to a time point 4 weeks later in that cycle.

** Time differences are measured from the previous treatment administered. A time deviation of ± 2 days is allowed for each visit, except for the week 1 visit in the first treatment cycle where a time deviation of ± 1 day is permitted. Sites must adhere to the schedule of events and visit windows and subjects must ensure they are available for those visits. However, if for practical reasons e.g. public holidays, a visit window cannot be met, a visit can be scheduled as close as possible to that visit window. However, any deviation from the visit schedule and its associated time windows will still be documented as a protocol deviation.

*** Full physical examination will include neurological assessment (including extraocular movements and cranial nerves) as well as assessment for muscle weakness. In addition, if the subject reports any symptoms related to Adverse Events of Special Interest (as detailed in the AESI Manual) a focused physical examination, to evaluate these symptoms will also be undertaken.

§ The ECG performed at screening is the baseline ECG. Laboratory and Anti-drug-antibody (ADA) test samples from screening are considered baseline values.

- 1 Depending on the duration of treatment effect, a maximum of 4 treatments is permitted.

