6.4.2.3 Safety

The secondary safety endpoints include:

1. Frequency, severity and causal relationship of AEs, SAEs and AESIs during the entire study period.
2. Antibody formation, evaluation pre-dose before each treatment, at 4 weeks after each treatment and at the final study visit.
3. Safety assessments by evaluating hematology, clinical chemistry, vital signs and ECGs as per study schedule (Section 2.1).

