7.2 Exclusion Criteria

Subjects who meet **ANY** of the following criteria are **NOT** eligible for this study:

- Previous treatment with any serotype of botulinum toxin for any indication within the 12 months prior to screening, or any planned treatment with botulinum toxin of any serotype for any reason during the trial (other than the investigational treatment).
- Known hypersensitivity to the study medication or its excipients.
- Any medical condition that may place the subject at increased risk due to exposure to botulinum toxin, including diagnosed myasthenia gravis, Eaton-Lambert syndrome, amyotrophic lateral sclerosis, profound atrophy or

ⁱWill be assessed at screening and at baseline visits.

ⁱⁱhttp://www.hma.eu/fileadmin/dateien/Human_Medicines/01-About_HMA/Working_Groups/CTFG/2014_09_HMA_CTFG_Contraception.pdf

weakness in the target muscles, or any other condition (at the investigator's discretion) that might interfere with neuromuscular function or contraindicate botulinum toxin therapy.

- Facial laser or light treatment, microdermabrasion, superficial peels or retinoid therapy within the 3 months prior to screening or planned during the study.
- Apart from the procedures specified above, previous treatment with any facial aesthetic procedure in the glabellar area (including chemical peeling, injection with biodegradable fillers,) within 12 months prior to screening or planned during the study.
- Previous insertion of permanent material in the glabellar area or planned during the study.
- Any surgery, or history of surgery, in the glabellar area including surgical removal of the *corrugator*, *procerus* or *depressor supercilii* muscles or a combination of these or scars in the glabellar area or such surgery planned during the study.
- Active skin disease/infection or irritation at the treatment area.
- Inability to substantially lessen glabellar frown lines even by physically spreading them apart.
- Use of a muscle relaxant within 2 weeks prior to screening or planned during the study.ⁱⁱⁱ
- Marked facial asymmetry or ptosis of eyelid and/or eyebrow, or current facial palsy or neuromuscular junction disorders as judged by the investigator.
- Pregnant, breastfeeding or planning to become pregnant during the trial.

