11.15.2 Antibody Test

Serum samples will be tested for the presence of antibodies to botulinum toxin using an Anti Drug Antibody (ADA) ELISA assay; initially only the last sample obtained from each study subject will be analyzed together with the pre-dose baseline sample. If a sample tests positive for anti-drug antibodies, the other samples from the subject will be analyzed to determine when antibodies developed. Serum samples which test positive for binding antibodies will subsequently be tested for neutralizing activity. Blood serum for ADA tests will be collected at screening, at the visit 4 weeks after treatment and at the end of cycle visit for each treatment cycle and will be stored for future analysis should the need arise, based upon the presence of ADA at the end of the study. Sample storage at -80°C is preferable, but samples can be stored at -20°C at sites if -80°C storage is not available. Samples will be stored (at [REDACTED].) until completion of the trial and will be destroyed thereafter.

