8.4.2 Baseline characteristics

The categorical baseline characteristics such as baseline ECG, pregnancy test results and antibody test sample collection (yes/no) at screening will be summarized using frequency counts for the FAS Population. Continuous baseline variables such as systolic blood pressure (mmHg), diastolic blood pressure (mmHg) and pulse rate (beats/min) will be summarised by descriptive statistics in the same way as continuous demographic variables for the FAS Population.

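### Antibody formation is summarised as presence at each time point; no planned statistic directly reports the rate of new antibodies among subjects negative at baseline

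*Protocol*

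**What the plan says.** Protocol 6.4.2.3 names the endpoint as "Antibody formation, evaluation pre-dose before each treatment, at 4 weeks after each treatment and at the final study visit". SAP 4.4 carries the same endpoint.

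For the analysis, Protocol 12.4.2 (secondary safety endpoint 2) states: "The presence of antibodies will be summarized by counts and percentages of subjects by treatment group and time point". For subjects with a positive sample it adds that "all analyzed samples will be analyzed descriptively by counts over time as well". SAP 8.7.3 repeats both sentences.

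The testing scheme is in Protocol 11.15.2 and SAP 8.7.3. In every subject, "initially only the last sample obtained from each study subject will be analyzed together with the pre-dose baseline sample". Then: "If a sample tests positive for anti-drug antibodies, the other samples from the subject will be analyzed to determine when antibodies developed". The footnotes to the schedule in Protocol 2.1 fix the baseline: "Laboratory and Anti-drug-antibody (ADA) test samples from screening are considered baseline values".

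Protocol 7.2 excludes "Previous treatment with any serotype of botulinum toxin for any indication within the 12 months prior to screening", so earlier users are not excluded. SAP 8.8.1 plans efficacy subgroups of previous users and naïve subjects. Among baseline characteristics, SAP 8.4.2 says that "antibody test sample collection (yes/no) at screening will be summarized using frequency counts".

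**The concern.** Formation is a change within a subject, from negative before the first dose to positive afterwards. Presence at a visit is a total across subjects. The two agree when everybody starts negative. They can differ when some subjects start positive, which the entry criteria allow.

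The other safety endpoints are tied to each subject's starting point. Adverse events have a treatment-emergent definition, laboratory and ECG data get shift tables, and vital signs get change from baseline (Protocol 12.4.2; SAP 8.7.2 and 8.7.4 to 8.7.6). Antibody results have no definition of conversion, no baseline-negative denominator and no baseline-by-post-dose table.

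Placebo subjects may receive BoNT/A-DP from cycle 2, so a placebo subject's last sample may follow active exposure. SAP 8.7 resets the baseline to cycle 2 day 0 for these subjects, but only for laboratory data, vital signs and ECG.

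At stake is how directly the report answers the immunogenicity question. Without a stated definition, the denominator and the handling of switchers would be left to whoever derives the rate, possibly after unblinding.

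**Working it through.** The documents give no antibody rate, precision or sample size for this endpoint, so there is no planned figure to reproduce. The check is arithmetic on a two-by-two table of baseline result by last-sample result.

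**Inputs**
- N = 525 planned active subjects (Protocol 12.1), taking every subject to have both results.
- B = number positive at baseline. Not given; assumed 0, 1, 2 or 5%, i.e. 0, 5, 10 or 26 subjects.
- C = conversions (negative to positive) and R = reversions (positive to negative). Not given; assumed 0 or 5 each.

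**Formulas**
- Positive at last sample: L = B − R + C. Presence = L / N.
- Conversion rate = C / (N − B).
- Ever positive: E = B + C, so C = E − B.

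**Results (illustrative)**

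| B | C | R | Presence at baseline | Presence at last sample | Conversion rate |
|---|---|---|---|---|---|
| 0 | 5 | 0 | 0% | 5/525 = 0.95% | 5/525 = 0.95% |
| 5 | 0 | 0 | 5/525 = 0.95% | 5/525 = 0.95% | 0/520 = 0% |
| 10 | 0 | 0 | 10/525 = 1.90% | 10/525 = 1.90% | 0/515 = 0% |
| 10 | 5 | 0 | 10/525 = 1.90% | 15/525 = 2.86% | 5/515 = 0.97% |
| 10 | 5 | 5 | 10/525 = 1.90% | 10/525 = 1.90% | 5/515 = 0.97% |
| 26 | 0 | 0 | 26/525 = 4.95% | 26/525 = 4.95% | 0/499 = 0% |

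**Reading the table**
1. With B = 0, presence and conversion are the same number.
2. With B > 0 and no reversions, persisting positives lift the post-dose percentage above the conversion rate. The baseline column shows the same positives.
3. With B = 10, C = 5 and R = 5, the by-time-point table shows no net change. From its two totals alone (10 and 10), anything from 0 to 10 conversions would fit.
4. The second planned output settles the number. The ever-positive subgroup in that row has E = 10 + 5 = 15 members, of whom 10 were positive at baseline, so C = 15 − 10 = 5.

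Step 4 gives the numerator. The denominator, baseline-negative subjects with a post-dose result, equals N − B only if nobody lacks a sample, and no planned output is specified to show it. The by-time-point percentages have a related gap: intermediate samples are tested only in subjects with a positive sample, and the plan does not say what those percentages are taken over.

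**The case against.** The strongest reply is that nothing is lost. Baseline and last samples are tested in every subject, positive subjects have their remaining samples tested to date the onset, and SAP 8.1 lists all subject data. The ever-positive subgroup identifies the converters, as step 4 shows. The endpoint is descriptive, with no test or decision rule. The table templates are in a separate document (SAP 1) and might already contain a cross-table. This all stands, and it limits the point to how the result is summarised.

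A reader might infer three stronger things, which the documents do not support.

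- *Baseline positives would be counted as formed in the trial.* The planned table is labelled presence, the screening sample is a tested time point, and no text calls a post-dose percentage a formation rate. That SAP 8.4.2 tabulates only sample collection does not show that the baseline result goes unreported; its natural place is the table in SAP 8.7.3.
- *Conversions offset by reversions would be invisible.* They can cancel in the by-time-point totals, but the size of the ever-positive subgroup recovers them.
- *The distortion is some multiple of the true rate.* Any such multiple comes from assumed prevalence and formation rates.

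The earlier glabellar study (Protocol 4.4.2.1) reported negative results before and after dosing in all subjects. That suggests a small effect. It does not establish zero prevalence in this EU and US population, where previous users may enter.

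**Conclusion.** The point holds as an improvement to the planned summary. It is not an error that hides conversions. The endpoint is formation, and the plan reports presence by group and time point plus counts over time in ever-positive subjects. A rate of new antibodies among baseline-negative subjects has to be derived by the reader.

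The size cannot be stated, because it depends on a baseline prevalence that the documents do not give. Over the assumed range of 0 to 5% positive at baseline, with no conversions or reversions, the last-sample percentage would run from 0 to 4.95% while the conversion rate stays at 0%. If nobody is positive at baseline, the effect is nil.

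**What to change.** In SAP 8.7.3:

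1. Make treatment-emergent antibody formation the main statistic: subjects negative at baseline with any positive post-dose result, divided by subjects negative at baseline with at least one post-dose result.
2. Add a baseline-by-post-dose shift table that shows baseline-positive subjects separately (persisting or lost) and is split by previous toxin use.
3. Report neutralizing results in the same way.
4. For placebo subjects who switch to BoNT/A-DP, use the sample taken before cycle 2 as baseline.
5. Keep the by-time-point counts as supportive, and state their denominator.

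Two consequences of the two-step testing should be written down. In a baseline-negative subject, intermediate samples are tested only if the last one is positive, so antibodies that appear and then disappear are not captured. For switchers, the sample before cycle 2 is tested only if another sample is positive; the SAP should say that switchers negative at both screening and last sample are taken as negative before cycle 2.

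SAP 9 says that the antibody analysis was changed from the protocol, yet the summary sentences are the same in both documents. The revision should say what changed.

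The cost is SAP wording and one table. No new samples are needed, and no new assays under the switcher convention above. Without that convention, stored pre-cycle-2 samples from switchers would have to be assayed, at most 175 on the planned placebo number.
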